The current study is designed to evaluate non-inferiority of TAF compared to TDF in regard to the proportion of subjects with HBV DNA levels below 29 IU/mL at Week 48. The durability of TAF compared to TDF in regard to the proportion of subjects with HBV DNA < 29 IU/mL at Weeks 96 and 144 will also be assessed in a double blind fashion. In addition to treatment naïve subjects, treatment experienced CHB subjects who are viremic and with elevated ALT levels at screening are included. This is based on given results from GS-US-174-0106 (ADV suboptimal responders) and GS-US-174-0121 (LAM-resistant subjects) which demonstrated in viremic patients comparable rates of HBV DNA suppression, as described below, in comparison to results in mostly treatment naïve subjects participating in pivotal studies GS-US-174-0102 (HBeAg-negative subjects) and GS-US-174-0103 (HBeAg-positive subjects). Given the unique properties of TAF (efficient delivery of the active moiety, TFV-DP, to HBV-infected hepatocytes with reduced systemic TFV exposures), this study will also evaluate the potential safety differences (e.g. renal- and bone-related complications) of TAF relative to TDF at Week 48 and long term comparative safety at Week 96 and 144, after which subjects will be further evaluated for longer-term safety and efficacy of TAF in an open-label TAF 25 mg QD extension phase through Week 384. The extension phase is important as it will enable the evaluation of subjects treated for the entire 384 week period with TAF as well as those who received 144 weeks of TDF initially in a double-blinded fashion followed by an additional 240 weeks of open-label TAF. The latter group will allow an ongoing assessment, including possible resolution, of any potential bone- and/or renal-related (or other) complications during TAF treatment that might have arisen under initial treatment with TDF.

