8. STATISTICAL CONSIDERATIONS

8.1. Analysis Objectives and Endpoints

8.1.1. Analysis Objectives

The primary objectives of this study are:

- To compare the efficacy of tenofovir alafenamide (TAF) 25 mg QD versus tenofovir disoproxil fumarate (TDF) 300 mg QD for the treatment of HBeAg-negative, chronic hepatitis B at Week 48 in treatment-naïve and treatment-experienced subjects. The primary efficacy parameter is the proportion of subjects with plasma HBV DNA levels below 29 IU/mL.
- To compare the safety and tolerability of TAF 25 mg QD versus TDF 300 mg QD for the treatment of HBeAg-negative, chronic hepatitis B at Week 48 in treatment-naïve and treatment-experienced subjects

The key secondary safety objectives of this study are as follows:

- To compare the safety of TAF 25 mg QD versus TDF 300 mg QD as determined by the percent change from baseline in hip and spine BMD at Week 48
- To compare the safety of TAF 25 mg QD versus TDF 300 mg QD as determined by the change from baseline in serum creatinine at Week 48

Other secondary objectives of this study are as follows:

- To compare the efficacy of TAF 25 mg QD versus TDF 300 mg QD for the treatment of HBeAg-negative, chronic hepatitis B in regard to the proportion of subjects with plasma HBV DNA levels below 29 IU/mL at Weeks 96, and 144
- To compare the efficacy of TAF 25 mg QD versus TDF 300 mg QD for the treatment of HBeAg-negative, chronic hepatitis B in regard to the proportion of subjects with plasma HBV DNA levels below 29 IU/mL (target not detected) at Weeks 48, 96, and 144
- To compare the biochemical (ALT normalization) response of TAF 25 mg QD versus TDF 300 mg QD for the treatment of HBeAg-negative, chronic hepatitis B at Weeks 48, 96, and 144
- To compare the serological response (loss of HBsAg with seroconversion to anti-HBs) of TAF 25 mg QD versus TDF 300 mg QD for the treatment of HBeAg-negative, chronic hepatitis B at Weeks 48, 96, and 144

- To compare the change in fibrosis as assessed by FibroTest[®] of TAF 25 mg QD versus TDF 300 mg QD for the treatment of HBeAg-negative, chronic hepatitis B at Weeks 48, 96, and 144
- To compare the incidence of drug resistant mutations of TAF 25 mg QD versus TDF 300 mg QD at Weeks 48, 96, and 144
- To compare the change from baseline in ophthalmologic findings by fundoscopic examination of TAF 25 mg QD versus TDF 300 mg QD at Weeks 24, 48, 72, 96, and 144 in a subset of subjects

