8.1.4. Other Endpoints of Interest

- The proportion of subjects with plasma HBV DNA < 29 IU/mL at Weeks 96 and 144
- The proportion of subjects with plasma HBV DNA < 29 IU/mL (target not detected) at Weeks 48, 96, and 144
- The proportion of subjects with ALT normalization (by central laboratory and AASLD criteria) at Weeks 48, 96, and 144
- The proportion of subjects with HBsAg loss at Weeks 48, 96, 144, 240, and 384

- The proportion of subjects with HBsAg seroconversion to anti-HBs at Weeks 48, 96, 144, 240, and 384
- The change from baseline in fibrosis as assessed by FibroTest[®] at Weeks 48, 96, 144, 240 and 384
- The incidence of drug resistant mutations at Weeks 48, 96, 144, 240, and 384
- The change from baseline in ophthalmologic findings by fundoscopic examination at Weeks 24, 48, 72, 96, and 144 in a subset of subjects
- The proportion of subjects with treatment-emergent proteinuria (by dipstick) at Weeks 48, 96, 144, 240, and 384

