8.5. Efficacy Analysis

8.5.1. Primary Analysis

The primary efficacy analysis will be conducted when approximately 390 randomized subjects complete 48 weeks of the double-blind treatment period or discontinue prematurely. A two-sided 95% confidence interval, based on the large sample theory adjusted for the randomization stratification factors (the adjusted Mantel-Haenszel proportions), for the difference (TAF – TDF) in the proportion of subjects who achieved HBV DNA $<$ 29 IU/mL will be used to compare the treatment groups. A non-inferiority will be declared if the lower bound of this confidence interval exceeds a non-inferiority margin of -0.10 . If non-inferiority is established, the lower bound of the 95% CI will be compared to 0; if the lower bound of the 95% CI is greater than 0, then superiority of TAF over TDF will be established using the same confidence interval. Details will be provided in the statistical analysis plan.

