8.5.2. Analyses of Other Endpoints of Interest

Continuous secondary endpoints will be summarized using conventional descriptive statistics (n, mean, standard deviation, median, Q1, Q3, minimum, and maximum) by treatment group and overall. A Wilcoxon rank sum test will be used to compare the treatment groups, in an exploratory manner.

Categorical secondary endpoints will be summarized by number and percentage of subjects that meet the endpoint. A two-sided Mantel-Haenszel test, controlling for the randomization strata, will be used to compare the treatment groups, in an exploratory manner. Missing data will be handled by the missing = failure approach.

For the incidence of drug resistant mutations, the missing = excluded approach will be employed.

An analysis of the China subpopulation will also be conducted when approximately 150 randomized and treated China subjects complete 48 weeks of double-blind treatment or discontinue prematurely to examine the consistency of the responses between the China subpopulation and the overall population.

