6.2.2. Analysis Methods for Secondary Efficacy Endpoints

The analyses for the secondary efficacy endpoints will be conducted using the FAS.

All the secondary efficacy endpoints involving proportions will be analyzed using the same statistical method ($M = F$) applied to the analysis of the primary efficacy endpoint. Sensitivity analyses will be performed using the $M = E$ approach as well.

The change from baseline in \log_{10} (HBV DNA) (IU/mL), \log_{10} (HBsAg) (IU/mL), and ALT will be summarized by visit using observed data (ie, missing will be excluded). In addition, the proportion of subjects with HBV DNA < 29 IU/mL, mean change from baseline in \log_{10} (HBV DNA) (IU/mL), \log_{10} (HBsAg) (IU/mL), and ALT (U/L) will be plotted with 95% CI over time using observed data for FAS.

Fibrosis assessed by FibroTest[®] at each visit and the change from baseline in fibrotest score will be summarized using descriptive statistics (sample size, mean, SD, median, Q1, Q3, minimum, and maximum) by treatment group. A shift table of fibrosis stage based on fibrotest score by visit will also be provided. Mean change from baseline in fibrotest score will be plotted with 95% CI over time using observed data for FAS. A listing of fibrosis assessment by FibroTest[®] will also be provided.

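### TAF-versus-TDF durability of HBV DNA suppression at Weeks 96 and 144 is compared only by percentages and an exploratory test of no difference; an adjusted difference with a 95% CI would answer the question better at little cost

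*Protocol*

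**What the plan says.** Protocol 1.3.2 sets out the Week 48 non-inferiority aim and then adds a further double-blind assessment, of "The durability of TAF compared to TDF in regard to the proportion of subjects with HBV DNA < 29 IU/mL"; the visits named for it are Weeks 96 and 144. Protocol 8.1.1 makes this a secondary objective, to compare the arms "in regard to the proportion of subjects with plasma HBV DNA levels below 29 IU/mL at Weeks 96, and 144". Protocol 8.1.4 lists the endpoint among the other endpoints of interest: "The proportion of subjects with plasma HBV DNA < 29 IU/mL at Weeks 96 and 144".

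Protocol 8.5.2 therefore governs the analysis. It provides a summary ("Categorical secondary endpoints will be summarized by number and percentage of subjects that meet the endpoint"), then a single inferential method ("A two-sided Mantel-Haenszel test, controlling for the randomization strata, will be used to compare the treatment groups, in an exploratory manner"), and finally a rule for incomplete data ("Missing data will be handled by the missing = failure approach"). The estimate with a margin appears only in 8.5.1, for Week 48: "A non-inferiority will be declared if the lower bound of this confidence interval exceeds a non-inferiority margin of -0.10". The synopsis adds only number and percentage for categorical secondary endpoints.

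The SAP supplied covers only the Week 48 analysis of subjects enrolled in China (SAP 1 and 2). SAP 6.2.2 says secondary proportions "will be analyzed using the same statistical method ($M = F$) applied to the analysis of the primary efficacy endpoint". In that SAP the primary method (6.1.2) is missing = failure counts and percentages, with no between-arm difference, confidence interval or margin. SAP 6 stops missing = failure summaries at Week 48, and SAP 6.2.1 leaves out Week 144. The 95% CIs plotted over time in SAP 6.2.2 are not said to be for the difference between arms.

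**The concern.** Durability relative to an active control is a question about how large a loss can be excluded. A test of no difference does not answer it. A large p-value may mean that the arms are close or that the data are too sparse to separate them. A small p-value may accompany a loss well inside 10 points. Only an estimated difference with an interval distinguishes these cases.

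At stake is how the later results read. If a p-value is the only inferential result, a loss as large as the Week 48 margin could be described as showing no significant difference. This becomes more likely if response rates fall at later visits, as they may when drop-out counts as failure, because the variance of a proportion grows as the rate moves from 91% towards 80%.

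**Working it through.** **Inputs.** 260 TAF and 130 TDF, 91% in both arms, margin 0.10, one-sided 0.025 (Protocol 8.8). 285 and 141 randomised outside China (SAP 1.2). The documents give no response rate for Weeks 96 or 144, so TDF rates of 85% and 80% are assumptions. Missing = failure keeps the denominators at the full arm sizes. All calculations are unstratified, whereas the planned test is stratified.

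**1. The plan's own figure.** SE = √[0.91 × 0.09 × (1/260 + 1/130)] = 0.0307. Power = Φ(0.10/0.0307 − 1.96) = Φ(1.293) = 90.2%. The stated 90% reproduces.

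**2. Test of no difference when TAF is truly 10 points worse (TDF 91%, TAF 81%).**
- Pooled rate = (260 × 0.81 + 130 × 0.91)/390 = 0.843.
- Null SE = √[0.843 × 0.157 × (1/260 + 1/130)] = 0.0390.
- SE under the true rates = √[0.81 × 0.19/260 + 0.91 × 0.09/130] = 0.0350.
- P(significant) = Φ[(0.10 − 1.96 × 0.0390)/0.0350] = Φ(0.671) = 74.9%, so 25.1% are non-significant.

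Exact binomial enumeration, using the Mantel-Haenszel chi-square with its N/(N − 1) factor, gives:

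| TDF rate | Non-significant, 260/130 | Non-significant, 285/141 | 95% CI lower bound above -0.10 (either size) |
|---|---|---|---|
| 91% | 24.6% | 20.8% | 2.1% |
| 85% (assumed) | 37.2% | 32.7% | 2.1% |
| 80% (assumed) | 43.5% | 39.8% | 2.2% |

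With a true 4.5-point loss (TDF 91%, 260/130), 38.7% of trials give a non-significant test while the 95% CI still includes a 10-point loss.

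**3. Two illustrative results (assumed counts, Wald CI, pooled z-test).**
- TAF 221/260 (85.0%) against TDF 118/130 (90.8%): difference -5.8 points, 95% CI -12.4 to +0.8, p = 0.11. Not significant, yet a 10-point loss is not excluded.
- TAF 246/260 (94.6%) against TDF 129/130 (99.2%): difference -4.6 points, 95% CI -7.7 to -1.5, p = 0.026. Significant, yet a 10-point loss is excluded.

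**4. How often the interval would exclude -10 points if the arms are equal.** Using the formula in step 1 at 260/130: 90.2% at a rate of 91%, 74.1% at 85% and 64.3% at 80%. At 285/141: 92.4%, 77.6% and 68.0%.

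**5. Week 144.** Protocol 3.1 and SAP 1.1 show that some subjects moved to open-label TAF at Week 96. Let f be the fraction of the TDF arm that switched, and assume that they take on the TAF rate. The TDF arm's rate becomes (TDF rate − 0.10f), and the expected difference shrinks from -0.10 to -0.10 × (1 − f). The fraction is not in the documents. By exact enumeration at 260/130 with a true 10-point loss, over TDF rates of 80% to 91%, the interval wrongly clears -0.10 in about 7–9% of trials at f = 25%, 18–24% at 50% and 34–45% at 75%, against about 2% with no switching.

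**The case against.** The strongest reply concerns status. The objectives say only that the arms will be compared. The endpoint lies outside the multiplicity procedure in Protocol 8.3, and 8.5.2 calls the test exploratory. No text makes a non-significant p-value a criterion of success. Percentages by arm are also reported, so a reader could compute a crude difference and interval. All of this stands and limits the point to a reporting improvement. It does not make a test of equality informative about durability.

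Three further limits also stand:
- The 10% margin is justified in 8.5.1.1 from Week 48 data only, so at later visits it is a reference line and not a validated margin.
- A SAP for the non-China Week 96 and 144 analyses was not supplied. It may already add an interval, which cannot be checked.
- At the only documented response rate and 285/141 subjects, the test would detect a 10-point loss about 79% of the time. The higher miss rates rest on assumed TDF rates.

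A reader might infer that the trial plans to claim continuing non-inferiority from a non-significant test, or that the test was chosen because it favours TAF. The documents support neither. They state no such hypothesis or reading rule, and the second example in the working shows that the test can also count against TAF when the loss is within 10 points.

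**Conclusion.** The point holds as a cheap improvement to an exploratory analysis. In the documents supplied, the durability comparison at Weeks 96 and 144 rests on percentages and a test of no difference, with no between-arm difference, interval or reference margin. A true loss of 10 points would be non-significant in about 25% of trials at 260/130 and 21% at 285/141 with TDF at 91%. The figures at 260/130 are 37% and 44% if the TDF rate is 85% or 80%. These results are unstratified, and the two lower rates are assumptions.

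It would be tempting to go further and apply the Week 48 decision rule unchanged to the whole full analysis set at both later visits. The documents do not support that at Week 144: subjects already moved to open-label TAF pull the arms together, which is anticonservative against a margin. Nor does the point touch the Week 48 primary analysis, which uses an interval against the margin and whose stated power reproduces.

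**What to change.** In Protocol 8.5.2 and the SAP for the later analyses:

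- **Week 96.** Report the stratum-adjusted TAF − TDF difference with two-sided 95% CI by the method of 8.5.1, on the full analysis set with missing = failure, and with missing = excluded as sensitivity. Read the lower bound descriptively against -0.10 as a supportive reference, noting that this margin was justified from Week 48 data.
- **Week 144.** Report the same difference and interval as the TAF-versus-TDF comparison only in subjects whose amendment kept them on double-blind treatment to Week 144. Define that group by amendment, not by who stayed on treatment. Present subjects moved to open-label TAF at Week 96 separately.
- **Interpretation.** State that a non-significant Mantel-Haenszel p-value is not evidence of maintained efficacy.

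The cost is a few sentences and reuse of the Week 48 method, plus a rule classifying subjects by amendment at Week 144. No new data or subjects are needed. The downside is that a wide interval at a later visit, particularly in the smaller Week 144 group, may not exclude -10% and would have to be reported.

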8.6. Safety Analysis

All safety data collected on or after the date that study drug was first dispensed up to the date of last dose will be summarized by treatment group (according to the drug received). Data for the pretreatment and treatment-free follow-up periods will be included in data listings.

8.6.1. Key Secondary Safety Analyses

The percent change from baseline in hip and spine BMD at Week 48 will be analyzed using an ANOVA model. The model will include treatment group as fixed effect. The details are provided in the Statistical Analysis Plan (SAP).

The change from baseline in serum creatinine at Week 48 will be analyzed using an ANCOVA model with baseline serum creatinine as a covariate, and treatment group as a fixed effect. The details are provided in the SAP.

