Final Week 24 results from GS-US-292-0102, a phase 2 study being conducted in HIV-1 treatment naïve subjects, demonstrated similar safety and tolerability of TAF vs. TDF when each is included as a component of STRs containing elvitegravir, cobicistat, and emtricitabine. At Week 24, significant differences were noted between arms in regard to smaller declines in hip BMD, estimated CL_{Cr} (Cockcroft-Gault), and changes in various biomarkers of bone and renal function which are suggestive of differences in bone and renal tolerability of TAF vs. TDF. Similar assessments are included in the present trial in HBeAg-negative, chronic HBV subjects, and the study is sufficiently powered to demonstrate a potentially superior safety profile for TAF relative to TDF in regard to these bone and renal parameters.

In summary, a 25 mg dose was selected for TAF for use in this non-inferiority trial based upon the safety profile for TAF in treatment naïve HIV-1-infected subjects from GS-US-292-0102, which utilizes a therapeutically equivalent TAF dose (10 mg as a component of the E/C/F/TAF STR), the viral suppression results in chronic HBV subjects in GS-US-320-0101 showing comparable rates of HBV DNA decline for a TAF 25 mg dose compared to TDF 300 mg (the approved dose for treatment of HBV), and the reduced systemic TFV exposures (~93%) seen with TAF relative to TDF 300 mg, when dosed at this level.

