6.2. Pretreatment Assessments

6.2.1. Screening Visit

Subjects will be screened within 45 days before Baseline to determine eligibility for participation in the study. The following will be performed and documented during the screening period:

- Obtain written informed consent
- Review of inclusion/exclusion criteria
- Obtain medical history, including HBV history
- Review concomitant medications
- Record any serious adverse events and all adverse events related to protocol mandated procedures occurring after signing of the consent form
- Complete physical examination including vital signs (blood pressure, pulse, respiration rate and temperature), body weight, and height

- ECG (subjects must rest quietly in the supine position for a minimum of 5 minutes prior to the recording)
- DXA scan of spine and hip (at sites in China with capability only). DXA scan will be performed at any time during the Screening period and should be completed at least 14 days prior to the first dose of the study drug, in order to ensure an acceptable pre-dose DXA scan
- Ophthalmologic assessment, including fundoscopic examination with slit lamp and retinal photographs (both eyes) (**substudy subjects only at select sites** - separate consent required) – to be performed at any time during the Screening period and prior to the first dose of the study drug
- Blood sample for serum chemistry and liver function tests, hematology, plasma HBV DNA, serum HBsAg (quantitative), HBV serology (HBeAg, HBeAb, HBsAg and reflex HBsAb), HIV-1, HDV, HCV, serum pregnancy test (for females of child-bearing potential), α -fetoprotein (AFP) and INR. An AFP > 50 ng/mL at Screening must have an appropriate evaluation (e.g. CT scan) in order to rule out HCC prior to being permitted to enter the study
- Estimated creatinine clearance (using the Cockcroft-Gault method)
- Urine sample for urinalysis

Subjects meeting all of the inclusion criteria and none of the exclusion criteria will return to the clinic within 45 days for randomization into the study. If the subject is deemed ineligible for this study by HBV serology (i.e. HBeAg-positive CHB), this information may be used to determine eligibility for GS-US-320-0110 (another Gilead Sciences Phase 3 study in HBeAg positive, CHB subjects; this study must also be IRB/EC approved at the participating center).

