8.3. Multiplicity Adjustments

The primary hypothesis of non-inferiority between TAF 25 mg QD and TDF 300 mg QD with respect to the proportion of subjects with HBV DNA < 29 IU/mL will be tested first. If non-inferiority is established, then multiplicity adjustments will be performed for the secondary endpoints with a fallback procedure using the following weights:

- a) Hip BMD (weight = 0.4)
- b) Spine BMD (weight = 0.2)
- c) Serum creatinine (weight = 0.4)

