8.8. Sample Size

With respect to the primary efficacy endpoint, a sample size of 130 for the TDF 300 mg group and 260 for the TAF 25 mg group will have 90% power to rule out the non-inferiority margin of 10% at a one-sided significance level of 0.025. This assumes a rate of 91% in the TDF 300 mg group and 91% in the TAF 25 mg group in the proportion of subjects with HBV DNA < 29 IU/mL. A similar response rate in the TDF group was observed in GS-US-174-0102 {[Marcellin et al 2007](#), [Marcellin et al 2008](#)}.

This sample size (n=260 for the TAF 25 mg arm, n=130 for the TDF 300 mg arm) also provides at least 90% power to detect a 1% difference in the percentage change from baseline in hip BMD at Week 48 (assuming a -1.17% change from baseline in TDF 300 mg arm and -0.17% change from baseline in the TAF 25 mg arm, with a common standard deviation of 2.20% and a two-sided $\alpha = 0.025$); a 77% power to detect a 1% difference in the percentage change from baseline in spine BMD at Week 48 (assuming a -1.69% change from baseline in the TDF 300 mg arm and -0.69% change in the TAF 25 mg arm, with a common standard deviation of 3.08% and a two-sided $\alpha = 0.025$); a 52% power to detect a 0.03 mg/dL difference in the change from baseline in serum creatinine at Week 48 (assuming a 0.04 mg/dL change from baseline in the TDF 300 mg arm and 0.01 mg/dL change from baseline in the TAF 25 mg arm, with a common standard deviation of 0.12). These assumptions were derived from studies GS-98-437, GS-98-438, GS-US-174-0102, GS-US-174-0103, and GS-US-174-0121.

For China, approximately 150 additional subjects (100 subjects TAF 25 mg QD and matched placebo of TDF 300 mg QD, and 50 subjects TDF 300 mg QD and matched placebo of TAF 25 mg QD) will be enrolled.

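### Protocol 1.3.3 claims adequate power for renal parameters while 8.8 gives 52% for serum creatinine; the Screening creatinine is also left out of the ANCOVA, where it could add a modest, uncertain gain

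*Protocol*

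**What the plan says.** **Power.** Protocol 1.3.3, after describing bone and renal differences seen in an HIV Phase 2 study, says that similar assessments are included here and that "the study is sufficiently powered to demonstrate a potentially superior safety profile for TAF relative to TDF in regard to these bone and renal parameters". Protocol 8.8 gives "a 52% power to detect a 0.03 mg/dL difference in the change from baseline in serum creatinine at Week 48". The Synopsis repeats the figure, and SAP 1.3 carries it over for the non-China subjects. The same section gives at least 90% for hip BMD and 77% for spine BMD. No other renal measure has a power figure.

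**Endpoint and model.** Serum creatinine is the only renal item among the key secondary safety endpoints in Protocol 8.1.3. Section 8.6.1 analyses its Week 48 change with an "ANCOVA model with baseline serum creatinine as a covariate, and treatment group as a fixed effect" and leaves details to the SAP. SAP 3.7.1 defines baseline as the last nonmissing value on or before Study Day 1, so a Day 1 value displaces the Screening value.

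**Data collected.** The Screening visit (Protocol 6.2.1) lists "Blood sample for serum chemistry and liver function tests, hematology, plasma HBV DNA, serum HBsAg (quantitative" among its assays. The Baseline visit (6.2.2) repeats serum chemistry before the first dose. The footnotes to Appendix 2 show that the chemistry panel includes creatinine.

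**The concern.** A reader of 1.3.3 would take a non-significant creatinine result as meaningful, because the text says the trial was large enough to show a renal advantage. On the figures in 8.8, a true difference of the assumed size would be missed almost half the time. A null result would then say little about renal safety.

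The second matter is efficiency. A single creatinine value carries short-term variation, so a second pre-dose value may explain more of the Week 48 variation. It is already scheduled, precedes dosing and cannot be affected by treatment. Leaving it out of the model may give up precision on the weakest-powered of the three key secondary endpoints.

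**Working it through.** **1. Reproducing the 52%.** Inputs from Protocol 8.8: "This sample size (n=260 for the TAF 25 mg arm, n=130 for the TDF 300 mg arm"; a difference of 0.03 mg/dL; and "0.01 mg/dL change from baseline in the TAF 25 mg arm, with a common standard deviation of 0.12". No alpha is printed for creatinine. Two-sided 0.025 is printed for hip and spine BMD and is used here.

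- Standard error = 0.12 × √(1/260 + 1/130) = 0.12 × 0.1074 = 0.01289.
- Noncentrality = 0.03 / 0.01289 = 2.33.
- Power = 53.1% by noncentral t, 53.4% by normal approximation. The stated 52% reproduces as an unadjusted two-group comparison.
- The same t method gives 97.6% for hip and 78.0% for spine, in line with the printed figures.

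Protocol 8.3 lists "c) Serum creatinine (weight = 0.4" in the fallback procedure. Assuming a family alpha of 0.05, creatinine's own share is 0.4 × 0.05 = 0.02, giving 49.7%. At the full 0.05, available if hip and spine both succeed, power is 64.1%. With the 285 and 141 non-China subjects actually randomized (SAP 1.2), power at 0.025 is 57.1%. None of these unadjusted figures reaches 80%. At alpha 0.025 and 260/130, 80% needs a residual SD of about 0.091, or about 687 subjects in total at SD 0.12.

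**2. Adding Screening creatinine.** The documents give no correlations, so these are assumptions. Let ρB and ρS be the correlations of Baseline and Screening with Week 48, and ρSB the correlation between Screening and Baseline. If 0.12 is the SD of the raw change, the variance at a single visit is σ² = 0.0144 / [2(1 − ρB)].

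- Baseline only: residual variance = σ²(1 − ρB²).
- Baseline and Screening as separate covariates: residual variance = σ²(1 − R²), where R² = (ρB² + ρS² − 2ρBρSρSB) / (1 − ρSB²).

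Example with all correlations 0.8: σ² = 0.0360. Baseline only leaves 0.0360 × 0.36 = 0.01296 (SD 0.1138). With both, R² = 0.256 / 0.36 = 0.711, leaving 0.0104 (SD 0.1020), a 20% reduction.

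| ρB | ρS | ρSB | Variance cut | Baseline only | Both, separate | Gain (points) |
|---|---|---|---|---|---|---|
| 0.70 | 0.70 | 0.70 | 17% | 60.8% | 69.8% | 9.0 |
| 0.80 | 0.80 | 0.80 | 20% | 58.1% | 68.7% | 10.7 |
| 0.90 | 0.90 | 0.90 | 22% | 55.5% | 67.8% | 12.2 |
| 0.80 | 0.80 | 0.90 | 9% | 58.1% | 62.8% | 4.7 |
| 0.85 | 0.80 | 0.88 | 4% | 56.8% | 58.9% | 2.1 |
| 0.85 | 0.748 | 0.88 | 0% | 56.8% | 56.8% | 0 |

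All rows use alpha 0.025 and 260/130. In the last row ρS = 0.85 × 0.88, so Screening carries nothing about Week 48 beyond what Baseline already carries.

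If 0.12 is instead the residual SD of the one-covariate model, equal correlations of 0.7, 0.8 and 0.9 raise 53.1% to 62.0%, 63.6% and 65.3%.

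**3. Averaging the two values.** Suppose the outcome stays change from Baseline and the mean of Screening and Baseline is the sole covariate. The residual variance is then 0.0144 − cov² / var(mean). With all correlations 0.8, cov = 0.0360 × (0.8 − 0.9) = −0.0036 and var(mean) = 0.0360 × 0.9 = 0.0324. That leaves 0.0144 − 0.0004 = 0.0140 and 54.4% power, against 58.1% for the planned model. At 0.7 and 0.9 the figures are 55.2% against 60.8%, and 53.7% against 55.5%. Averaging looks attractive only if the outcome is taken to be the Week 48 value itself. A change score needs Baseline in the model.

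**The case against.** - **The 52% is disclosed.** It is printed in the Synopsis, in 8.8 and in SAP 1.3, and 1.3.3 is a dose-rationale section whose preceding sentence names hip BMD, estimated creatinine clearance and biomarkers, not serum creatinine. This limits the harm. It does not support the claim: Cockcroft-Gault clearance is computed from serum creatinine, and no other renal measure has a power figure.
- **One pre-dose covariate is standard.** This stands. The planned ANCOVA is valid and prespecified and raises no bias or Type I error problem. The omission is a missed efficiency, not an error.
- **The gain may be nil.** This also stands. Screening can precede Baseline by up to 45 days and may predict Week 48 less well. The larger gains require it to predict equally well.
- **Little may be left to amend.** SAP section 2 says the non-China Week 48 analysis has been done, so adding a covariate there would be post hoc. The supplied SAP covers China only and summarizes creatinine descriptively (7.4.2). The SAP holding the ANCOVA details is not among the documents.

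A reader might infer that the single covariate is why power is 52%. It is not: 52% follows from the effect size, SD and sample size with no covariate, and the planned model may already give about 56 to 61% under equal correlations of 0.7 to 0.9.

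**Conclusion.** The conflict between Protocol 1.3.3 and 8.8 is established from the text and needs no assumption about correlations. The protocol's own power for its one renal key secondary endpoint is 52%, and 53.1% on recalculation.

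The covariate point holds as an inexpensive possible improvement of uncertain size. The gain is 0 points if Screening adds nothing once Baseline is known, 2 to 5 points in intermediate cases, and about 9 to 12 points under equal correlations of 0.7 to 0.9 (from 56–61% to 68–70%). All of this assumes 260/130, a difference of 0.03, SD 0.12 for the raw change and alpha 0.025.

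Two stronger readings are not supported. One is that adding Screening creatinine would make the renal claim true: no case tried reaches 80% at alpha 0.025. The other is that creatinine is the trial's only renal key endpoint throughout: that is so in the protocol, but SAP 1.1 and 7.11 add treatment-emergent proteinuria, with no power figure.

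**What to change.** 1. **Protocol 1.3.3:** limit the adequacy claim to the BMD endpoints and state the 52% for serum creatinine. In 8.8, print the alpha used for creatinine. Cost: two short text edits.
2. **Protocol 8.6.1, and whichever SAP carries the ANCOVA, only where that analysis is still to be run:** before unblinding, prespecify Screening creatinine as a second, separate covariate alongside Baseline creatinine, with the endpoint unchanged. Do not replace Baseline with the mean of the two. State which Screening value is used after a retest, and what is done if the Day 1 value is missing, since the SAP baseline definition would then pick up the Screening value. Cost: one degree of freedom, and no new data or visits.

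The completed non-China Week 48 analysis should stay as prespecified. The China SAP needs no covariate change while its creatinine analysis is descriptive.
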